14.2 Institutional Review Board

This protocol will be reviewed by the National Dental PBRN Central Institutional Review Board (IRB). The UAB IRB for Human Use serves as the National Dental PBRN Central IRB.

Once the local institution has decided to use the National Dental PBRN Central IRB review, the National Dental PBRN Central IRB is the IRB responsible for the review of the protocol. The National Dental PBRN Central IRB then performs all future continuing protocol and informed consent reviews and amendment (new protocol version) reviews. Additionally, when recruitment and/or educational materials are to be used by all participating local institutions, the National Dental PBRN Central IRB will review and approve the language. The Central IRB also reviews unanticipated problems distributed by the Administrative Unit to local institution PIs.

Once the National Dental PBRN Central IRB has approved a protocol, local institutions are able to perform a Local Context Review and open the protocol in a shorter time than required by the traditional local institution IRB review process. Once the decision to open the protocol has been made, local institutions have the prerogative to use the National Dental PBRN Central IRB review or conduct their own local review on a protocol-by-protocol basis. If an RAS or other local institution elects not to use the National Dental PBRN Central IRB, the protocol, consent form(s), recruitment materials and all participant materials will be submitted to the RAS or other local institution IRB for review and approval.

Approval (either centrally for those regions who agree to central approval, or regionally for those who do not) of both the protocol and the consent form must be obtained before any participant is enrolled. Any amendment to the protocol will require review and approval by the IRB before the changes are implemented in the study.

The National Dental PBRN Central IRB approved sample ICF will contain locked sections that may not be revised and unlocked sections that may be revised or added to by the Local Context Reviewer. The revisions or additions should be made to comply with state and local laws; professional and community standards; institutional policies, such as applying the institution's letterhead and adding local contact information; and the needs of differing populations. However, no content should be deleted, no additions or modifications should be made that might change the meaning of any sections, and no

“wordsmithing” may be done to the locked sections of the ICF. The local institution PI will provide a redline version of the sample ICF, incorporating local institution requirements, to the Administrative Unit for review PRIOR to submission to his/her local institution.

14.3 Informed Consent Process

Informed consent is a process that is initiated prior to the individual agreeing to participate in the study and continues throughout study participation. Extensive discussion of risks and possible benefits of study participation will be provided to participants and their families, if applicable. If required by the responsible IRB, a consent form describing in detail the study procedures and risks will be given to the participant. Consent forms will be IRB-approved, and the participant is required to read and review the document or have the document read to him or her. The investigator or designee who has received human subjects training will explain the research study to the participant and answer any questions that may arise. The participant will sign the informed consent document or give verbal approval of the consent process (depending upon central or regional IRB requirements) prior to any study-related assessments or procedures. Participants will be given the opportunity to discuss the study with their surrogates or think about it prior to agreeing to participate. They may withdraw consent at any time throughout the course of the study. A copy of the informed consent document will be given to participants for their records. The rights and welfare of the participants will be protected by emphasizing to them that the quality of their clinical care will not be affected if they decline to participate in this study.

The consent process will be documented in the clinical or research record.

Participating practices will designate who will execute informed consent for the study. In most cases this will be the dentist practitioner(s). Any personnel who will be assigned to obtain informed consent will be defined as designee and will complete required IRB training. Informed consent will be obtained in the practice prior to enrolling a patient into the study.

14.4 Exclusion of Women, Minorities, and Children (Special Populations)

The population is being restricted to individuals aged 18 years or older in order to eliminate a potentially confounding variable that could be quite significant in stability – facial growth. Based upon the results of this study, adolescents could be targeted for a future study.

14.5 Participant Confidentiality

Participant confidentiality is strictly held in trust by the investigators, study staff, and the sponsor(s) and their agents.

The study protocol, documentation, data, and all other information generated will be held in strict confidence. No information concerning the study or the data will be released to any unauthorized third party without prior written approval of the sponsor.

Practitioners and patients will be assigned unique identification numbers, which will be used to maintain study records and organize data transcripts. A file or database at the CC linking practitioners' and patients' names with their unique identification number will be password-protected.

The study monitor and other authorized representatives of the sponsor may inspect all study documents and records required to be maintained by the investigator, including but not limited to, dental records (e.g., office, clinic, or hospital) for the study participants. The clinical study site will permit access to such records.

15 DATA HANDLING AND RECORD KEEPING

The investigators are responsible for ensuring the accuracy, completeness, legibility, and timeliness of the data reported. All source documents should be completed in a neat, legible manner to ensure accurate interpretation of data.

Only study personnel (i.e., GPI, SPI, Co-I's, RCs, CC personnel) will have access to the study data elements in the study database as described in Section 15.3 Types of Data. Study personnel will include those who are on the approved IRB study protocol. All study personnel will have completed the required training elements for human subjects research certification.

15.1 Data Management Responsibilities

Data collection and accurate documentation are the responsibility of the study staff under the supervision of the SPI. All CRFs must be reviewed by the RC and data entry staff, who will ensure that they are accurate and complete. All practices will be trained on de-identifying and transmitting cephalometric x-rays and intra-oral frontal photos in a standardized manner, in order to assure the quality and integrity of the images. Unanticipated problems must be reviewed by the SPI or GPI.

Staff at the RAS will receive pCRFs from practitioners and will enter data into the web system. For the pCRFs that are to be used as source documents (see Section 12), the RAS staff will ensure the forms are completed, and they will be maintained at the RAS. The RAS staff will ensure the data are entered and the discrepancies generated by the system are resolved in a timely fashion based on study requirements. The RAS staff will work with practitioners to clarify any data issues and maintain a tracking log for the data changes. To aid the data collection and data entry activities, the CC will provide pCRF completion and electronic data entry guidelines.

15.2 Data Capture Methods

Study-specific pCRFs will be developed to include fields for all data elements required for participant assessments. A Web-based system will be used for the upload and storage of the cephalometric x-ray and intra-oral frontal photographs. All data from pCRFs will be entered into a Web-based data collection system to ensure that all required data are collected in the study database. As most fields will require a categorical response and some fields will ask for a numeric response, the data field in the database will be programmed to allow only certain values and ranges so that data entered from the web system can be validated and data errors be corrected. Reports and tools will be developed to help monitor the visit and data activities. Reports with a summary of data completion by participants will be made available on the network web site.

After the paper data collection has been completed for a patient at enrollment and at each follow-up visit, study materials for the patient will be placed in a secure location. Participating practices will maintain a patient participant log with the name of the patient corresponding to the study ID number printed on the CRFs. After completion of a study

visit, the practitioner will sign the pCRFs (if necessary), and the designated staff member will transmit the pCRFs to RCs.

15.3 Types of Data

Data for the present study consist of the following:

- Practitioner level data from the National Dental PBRN enrollment questionnaire and practitioner characteristics form;
- Patient characteristics data from baseline/enrollment data collection form;
- Patient-reported treatment preference, treatment compliance, and patient satisfaction data on baseline and follow-up visit data collection forms;
- Patient clinical data, and treatment-related data on baseline and follow-up visit data collection forms;
- Cephalometric x-rays and intra-oral frontal photographs; and
- Unanticipated problems data.

15.4 Schedule and Content of Reports

Reports to monitor enrollment will be produced every two weeks during the patient enrollment period, until enrollment targets are attained and enrollment is closed. These reports will provide accrual information in aggregate and by important data variables of interest (e.g. extraction status) and will also contain separate sections regarding patient accrual by practitioner.

Reports to monitor patient participation will be produced every three months after enrollment is closed. These reports will provide ongoing monitoring of patient participation during the active phase of treatment, and will contain information on when the patients are expected to begin the retention stage of treatment and/or final follow-up.

Patient participation reports will also be produced every three months for patients who enter the retainer use phase of their treatment. Data from these reports will be closely monitored, and futility analyses will be performed as needed. In addition, every six months a report will be produced for each individual practice that includes the practice's attrition rate and a comparison to the overall attrition rate for the study. These reports will be made available to the practitioners. For patients who are lost to follow-up, reports to assess reasons for loss will be produced after data has been obtained following the data collection period for each study follow-up assessment.

Medical Monitor reports will be produced at six months after study initiation until enrollment is closed, and then annually thereafter, and may be produced more frequently at the request of the NIDCR Medical Monitor. Data elements for inclusion in the Medical Monitor reports are stated in Section 9, Study Oversight. In addition to enrollment and retention reporting, the Medical Monitor reports will contain safety data as well as frequencies and descriptive statistics for primary outcome variables and key

variables, and quality management findings. The identification of key variables will be determined by the SPI and other study team members.

As portions of the study objectives can be addressed at the end of recruitment and at the end of active treatment, it is anticipated that some full analyses will be performed after each phase of data collection is complete. Interim analysis reports that address objectives requiring all study data to be collected will be produced at the discretion of the CC Statistician, in consultation with the SPI, and other study team members. The content of these reports will be determined by the CC Statistician, in consultation with the SPI, and other study team members.

The procedure for locking the database prior to final analysis will be detailed in Section 13 of the study DMP, in accordance with the Westat CCs Standard Operating Procedure (SOP) DSD-001: Development of a Data Management Plan and SOP DSD-405: Data Lock. Briefly, the Oracle Clinical (OC) data will be locked and the final SAS datasets will be generated at the end of the study. Prior to locking the database, the Clinical Data Manager (CDM) or designee will ensure all data are complete and clean. Then, the CDM will obtain approval from the Project Manager to proceed with the data lock. The CDM will then direct the Database Development Manager to lock the database. The date and time of database lock will be documented. All team members will receive written notification from the CDM or designee when the database lock is complete.

No masking or coding is anticipated for this study.

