3.2 Study Outcome Measures

The primary outcome measure to determine success of treatment will be overbite at the end of treatment. Overbite will be measured in two ways. The first method is to record whether the incisors have positive overlap at the end of treatment, which indicates success. This will be judged from the frontal photographs at all three time points (baseline/enrollment, end of active treatment, and one year after end of active treatment). Second, using lateral cephalograms, the overbite will be measured relative to a standardized reference line (for example, occlusal plane), at two time points. At the first time point, we will see that relative to occlusal plane, the initial overbite is negative (no incisal overlap), and the distance between the maxillary and mandibular incisor tips can be measured in millimeters perpendicular to the occlusal plane. At the second time point, the final overbite should be positive (incisal overlap), and this overlap can be measured in millimeters perpendicular to the occlusal plane. Based on the measurements from the initial and final cephalograms, we will assess whether the overbite has been treated successfully (positive incisal overlap), as well as how much the overbite has improved (in millimeters).

The primary measure to determine stability of treatment ascertained one year after removal of orthodontic appliances is the overbite measurement. Since a cephalogram will not be taken one year after the end of treatment, this measurement will need to be assessed from the photographs. Overbite will be measured in two ways. The first is the dichotomous assessment of incisal overlap at the follow-up time; this will be performed in the same manner as stated in the preceding paragraph. A positive incisal overlap will be considered stable. The second method will be performed by utilizing the proportions of teeth in order to determine how much overbite change has occurred (see Appendix C). The orthodontist will be asked to measure the height of the right maxillary central incisor at the time of deband and at the final visit. Using this measurement, along with the end-of-treatment and follow-up photos, the overbite can be calculated at each time point, as well as the amount of overbite change.

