11.3 Final Analysis Plan

Analysis plan for Primary Objectives:

Primary objective #1 is to estimate the proportion of patients who are successfully treated. As described in section 3.2 (outcome measures), successful treatment is defined as occurring when patients have positive overlap at the end of treatment; this will be calculated with a 95% confidence interval.

Though not an explicit hypothesis, we expect those that are “successfully” closed will have had a smaller distance between the maxillary and mandibular incisor tips prior to treatment, i.e., at enrollment, than those not successfully closed. We will calculate the mean distance improved separately for those successfully treated and those not. It may be that those not successfully treated had more improvement than those who were successfully treated (if the former had a greater distance that needed to be corrected) and we want to capture this. Thus, as an additional but secondary measure of improvement, we will also calculate mean and median distance improved as descriptive measures.

Primary objective #2 is to estimate, among patients who are successfully treated, the proportion of patients whose treatment is stable. As described in section 3.2 (outcome measures), stability will be assessed one year after end of active treatment. The primary measure (strictest, most conservative classification) will be among patients who are determined to have been successfully treated at end of active treatment (having closed their AOB), what proportion of these have positive overlap at the one-year follow up time. This proportion will be estimated with a 95% confidence interval. Additional assessments of stability will include the proportion of all who had improvement in overbite (positive increases) during retention, no change in overbite during retention, and worsening of overbite (negative increases) during retention. We will calculate these mean and median changes as descriptive measures.

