The cephalometric x-rays and intra-oral frontal photographs obtained as part of routine orthodontic care before treatment and at the time of appliance removal will be used for this research. Practitioners will obtain an additional intra-oral frontal photograph at the time of appliance removal and two other intra-oral frontal photographs at the Final Study Visit (approximately one year after appliance removal/end of active treatment). Practitioners will be asked to de-identify the x-rays and photos and upload them electronically to a central data collection site created and maintained by the CC. De-identification procedures will be detailed in the Practice Training Manual. The RCs will be asked to verify that x-rays and photographs uploaded are de-identified and of good quality. At the end of each data collection period, the SPI or designee will review the x-rays and photographs to measure overbite, mandibular plane angle, and incisor angulation. The related quality management procedures will be specified in the MOP. The measurements obtained will be used to assess the study outcome measures.

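### The primary-outcome images are read by the study lead or a designee, period by period and without stated masking, so reader drift or expectation could bias the stability proportion and the modality comparisons

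*Protocol*

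**What the plan says.** Section 13 names the reader and the timing: "At the end of each data collection period, the SPI or designee will review the x-rays and photographs to measure overbite". It gives the purpose as "The measurements obtained will be used to assess the study outcome measures" and leaves control of the readings to another document: "The related quality management procedures will be specified in the MOP". On the images themselves it says "Practitioners will be asked to de-identify the x-rays and photos and upload them electronically to a central data collection site".

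Section 15.4 ends with "No masking or coding is anticipated for this study".

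Section 3.2 makes the success outcome a yes/no reading of incisor overlap: "This will be judged from the frontal photographs at all three time points". For stability the photographs are the only images: "Since a cephalogram will not be taken one year after the end of treatment, this measurement will need to be assessed from the photographs". Section 11.3 defines the stability estimate among patients closed at end of treatment, asking "what proportion of these have positive overlap at the one-year follow up time".

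**The concern.** Both primary outcomes are threshold readings, and the stability estimate needs two of them per patient. The end-of-treatment reading decides who is in the denominator, and the one-year reading decides who counts as stable. Under section 13 these fall in different reading sessions. If the reader, or a change of designee, moves the point at which overlap is called present, the stable proportion moves for the whole cohort. The confidence interval does not show it.

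The reader is also not shielded from expectation:
- Section 15 gives the SPI access to the study data elements, and section 15.3 lists treatment-related data among them.
- Section 15.4 plans full analyses after each phase, so end-of-treatment results can be known before the one-year images are read.
- Section 2.1 records directional views: surgery and extraction may be more stable, conventional treatment may be prone to relapse, and aligners have limitations.
- Section 11.4.2 then compares success and stability across those same modalities.

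**Working it through.** **1. The plan's precision target.** Section 11.2 asks for 10% precision, 3 patients per practitioner and an ICC of 5%.

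- Design effect: 1 + (3 − 1) × 0.05 = 1.10.
- At 50%: n = 1.96² × 0.5 × 0.5 / 0.05² × 1.10 = 422.6, against 422 stated.
- At 60, 70, 80 and 90% the same formula gives 405.7, 355.0, 270.4 and 152.1, against 406, 355, 271 and 153.

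So the 10% is the full interval width, and the target is about ±5 points.

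**2. A drift between sessions, in millimetres.** The protocol gives no reader error and no overbite SD. Assume one-year overbite is normal with SD 1.5 to 2 mm, the end-of-treatment reading is held fixed, and the one-year threshold moves by 0.25 mm. The shift in the stable proportion is about φ(z) × 0.25 / SD, where z is the normal quantile of the true stable proportion.

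| True stable | φ(z) | SD 1.5 mm | SD 2 mm |
|---|---|---|---|
| 50% | 0.399 | 6.6 points | 5.0 points |
| 70% | 0.348 | 5.8 | 4.3 |
| 80% | 0.280 | 4.7 | 3.5 |
| 90% | 0.175 | 2.9 | 2.2 |

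**3. The same question as misreading.** Assume the one-year reader calls a fraction d of truly overlapped cases open. With S the true stable proportion, the observed proportion is o = S(1 − d), the bias is S × d, and the standard error is √(o(1 − o) × 1.10 / 422).

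| d | Bias in points at S = 50 / 70 / 90% | Coverage of the 95% interval |
|---|---|---|
| 2% | 1.0 / 1.4 / 1.8 | 93 / 91 / 81% |
| 5% | 2.5 / 3.5 / 4.5 | 83 / 69 / 29% |
| 10% | 5 / 7 / 9 | 50 / 19 / 1% |

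**4. Modality comparisons.** Section 11.4.1 plans 110 per group, so the effective size is 110 / 1.10 = 100. Assume equal true rates (50% or 70%) and a reader shift between two modalities. A shift of 2, 5 or 10 points raises the false-positive rate from 5% to about 6%, 11 to 12%, and 29 to 32%.

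The values of d, the 0.25 mm, the SDs and the modality shifts are all assumptions. The tables show what a given reading error would do, not how large it will be.

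**The case against.** The masking sentence closes a paragraph on interim reports and database lock and does not mention images. Read for every process, it would clash with the participant codes in sections 2.3.1 and 14.5. A reader might infer that the protocol forbids masked image reading. The documents do not settle that, because a meaning limited to reports and datasets is plausible. What stands is that the sentence is worded for the study, and nothing else in the protocol masks the reader. De-identification removes identity, but is not said to hide visit or treatment.

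Control of the readings is deferred to the manual of procedures, so the absence of calibration or repeat reads cannot be claimed. Masked reading there would, however, conflict with the broad sense of the section 15.4 sentence.

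A reader might also infer that visit and session are completely confounded. That goes too far. Section 13 does not say end-of-treatment photographs are never viewed again, and the change calculation in section 3.2 uses both sets.

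Nor is any bias beyond examination. The end-of-treatment cephalogram, and the practitioner and patient reports of closure described in section 7.1, could reveal gross drift. The check is partial, because there is no cephalogram at one year and those reports are unmasked too.

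Finally, the millimetre illustration is largest at 50% stable. Section 11.2 cites reported stability of 65% to 100%, while calling those rates likely overestimated and planning on 50%. Clear-cut cases are little exposed.

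**Conclusion.** The point holds as an avoidable weakness in how the primary outcomes are read. As written, the reader may know treatment and visit, and the two readings behind the stability estimate are made in different sessions. The resulting bias cannot be sized from the protocol. Under the assumed 0.25 mm drift it reaches the planned ±5 points at 50% stable (5.0 to 6.6 points) and stays below it at 80% (3.5 to 4.7) and 90% (2.2 to 2.9). The documents do not support saying that bias is certain, that masking is forbidden, or that no other data could expose a problem. The sample size is not affected.

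**What to change.** Amend section 13 and the closing sentence of section 15.4 together:

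- The coordinating center assigns random codes to the images in its repository.
- The reader sees no treatment data and no visit label.
- After the final visit period, one reader reads all end-of-treatment and one-year photographs together in random order.
- This masked reading governs the primary success and stability analyses, including who enters the stability denominator. Any earlier reading serves interim reports only.
- If the section 15.4 sentence was meant only for reports or datasets, say so.

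The last rule on governing readings is needed because otherwise there would be two end-of-treatment readings and no rule for choosing between them.

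The cost is the coding work and the re-reading of end-of-treatment photographs, for about 840 × 0.90 = 756 patients on the plan's own attrition figure. The governing success result also waits until the final visit period closes. No extra patient procedure, reader or enrolment is needed. Some images may still reveal the treatment, so masking will be incomplete, but the mixed order still removes the link between session and visit.
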